## 6 SELECTION AND WITHDRAWAL OF SUBJECTS

### 6.1 Inclusion criteria

To be eligible to participate in this study, all of the following criteria must be met:

1. An Institutional Review Board (IRB)/Independent Ethics Committee (IEC) approved written Informed Consent form is signed and dated by the subject or legal representative. The
2. Subject/legal representative is considered reliable and capable of adhering to the protocol (eg, able to understand and complete questionnaires), visit schedule, or medication intake according to the judgment of the Investigator.
3. Subject is at least 18 years old at the Screening visit.

4. Female subjects must be either postmenopausal for at least 1 year, surgically incapable of childbearing, or effectively practicing an acceptable method of contraception (either oral/parenteral/implantable hormonal contraceptives, intrauterine device, or barrier and spermicide). Abstinence only is not an acceptable method. Subjects must agree to use adequate contraception during the study and for at least 10 weeks (or [for participating countries of the EU – 5 months in accordance with the Summary of Product Characteristics, SPC] longer if required by local regulations) after the last dose of study treatment. Male subjects must agree to ensure they or their female partner(s) use adequate contraception during the study and for at least 10 weeks (or [for participating countries of the EU - 5 months in accordance with the SPC] longer if required by local regulations) after their last dose of study treatment.
5. Subjects must have a documented diagnosis of adult-onset axSpA and meet the ASAS criteria for axSpA (not including family history and good response to NSAIDs; see Appendix 18.1).
6. Subjects must have had back pain for at least 12 months before Screening.
7. Subjects must NOT have sacroiliitis defined by mNY criteria (see Appendix 18.2) (bilateral  $\geq$ Grade 2; unilateral  $\geq$ Grade 3) on SI joint x-rays (based on central reading of x-rays, within the last 12 months from Baseline).
8. Subjects must have active disease as defined by each of the following at Screening and Baseline:
  - BASDAI score  $\geq$ 4
  - Spinal pain  $\geq$ 4 on a 0 to 10 NRS (from BASDAI item 2)

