## 9.1 Assessment of efficacy variables

### 9.1.1 ASDAS

The ASDAS is comprised of a number of assessments which are scored by the subject and physician and multiplied by a proven formula (van der Heijde et al, 2009) as listed:

0.121 x Back pain (BASDAI Q2 result, see Section 9.1.5)

0.058 x Duration of morning stiffness (BASDAI Q6 result)

0.110 x PGADA (see Section 9.1.13)

0.073 x Peripheral pain/swelling (BASDAI Q3 result)

0.579 x (natural logarithm of the (CRP [mg/L] + 1))

Back pain, PGADA, duration of morning stiffness, peripheral pain/swelling and fatigue are all assessed on a numerical scale (0 to 10 units) (Lukas et al, 2009).

The variables related to ASDAS disease activity are defined as follows:

- ASDAS-Inactive Disease (ASDAS-ID): ASDAS <1.3
- ASDAS-Low Disease (ASDAS-LD): ASDAS  $\geq$ 1.3, <2.1
- ASDAS-High Disease Activity (ASDAS-HD): ASDAS  $\geq$ 2.1,  $\leq$ 3.5
- ASDAS-very High Disease Activity (ASDAS-vHD): ASDAS >3.5

The variables related to ASDAS improvement are defined as follows:

- ASDAS-Clinically Important Improvement (ASDAS-CII): ASDAS reduction (improvement) of  $\geq$ 1.1 relative to Baseline
- ASDAS-Major Improvement (ASDAS-MI): ASDAS reduction (improvement) of  $\geq$ 2.0 relative to Baseline

The ASDAS will be calculated at Screening, Baseline, Weeks 2, 4, 8, 12, 16, 20, 24, 28, 32, 36, 40, 44, 48, 52/WD, and Week 156/SFE-WD.

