### **14.3 Planned efficacy analyses**

The primary efficacy variable measurement for this study is based on ASDAS-MI response at Week 52. The associated primary outcome of the study will be defined as a composite endpoint that is achieved if a subject fulfills the following 2 components:

1. Remain in the study and on the double-blind study treatment through 52 weeks
2. Achieve an ASDAS-MI response at 52 weeks

For simplicity, this primary efficacy variable will be referred to as ASDAS-MI response at Week 52. However, the composite definition as described above will apply when this endpoint is analyzed. The primary analysis for this endpoint will be based on logistic regression. The odds ratio of the ASDAS-MI responder rates at Week 52 will be estimated and tested between treatment groups using a logistic regression model with factors of treatment group, region, and MRI/CRP classification (MRI+/CRP+; MRI+/CRP-; MRI-/CRP+). If the logistic regression

model is unable to converge, then the MRI/CRP classification variable may be dropped from the model to facilitate convergence. The study design is likely to result in some sites with a small number of enrolled subjects. The use of region as a stratification variable and as a factor in the model is intended to combine study centers in similar geographic regions. The geographic regions to be used will be defined in the IXRS and in the SAP. Given the composite endpoint definition described above, there will be no missing data for the primary endpoint, as subjects that discontinue the double-blind study treatment prior to Week 52 or who do not have an ASDAS-MI status at Week 52 are considered nonresponders to the double-blind study treatment.

As described in Section 6.3, subjects who discontinue the double-blind study treatment will not necessarily be withdrawn from the study. In an attempt to minimize missing data, efforts will be made to continue to collect safety and efficacy data on these subjects through study completion. Sensitivity analyses will be performed to evaluate the impact of missing data on the analysis of the primary efficacy variable (see Section 14.8).

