Additionally, change from Baseline in SI joint SPARCC score at Week 12 is a continuous secondary efficacy variable. The same MI procedure specified as the main analysis approach for BASDAI and BASFI will be used to account for missing SPARCC data. However, it should be noted that, unlike BASDAI and BASFI, SPARCC score will not be measured at any time points between Baseline and Week 12, meaning that those are the only 2 time points that can be considered in the evaluation of SPARCC score at Week 12. Comparisons between treatment groups will be made using an analysis of covariance (ANCOVA) model on the imputed data set. The model will include Baseline score, treatment group, region, and MRI/CRP classification.

The ASAS40 response at Week 12 and Week 52 are responder secondary efficacy endpoints. (For Canada and any other country where applicable or where requested by Regulatory Authorities, the ASAS40 response at Week 12 is the primary efficacy variable; the ASAS40 response at Week 52 and the ASDAS-MI response at Week 52 are secondary efficacy variables). As a responder variable, ASAS40 will be analyzed using logistic regression based on a model similar to the one described for the primary analysis.

The number of subjects with new onset post-Baseline AU or new AU flares through Week 52 is a categorical secondary efficacy endpoint for all regions. Subjects with a new event at one or more visits post-Baseline will be classified as having had a flare, subjects without new events at all visits post-Baseline will be classified as not having had a flare. As a dichotomous outcome variable, treatment groups will be compared for differences using logistic regression based on a model similar to the one described for the primary analysis.

The comparison of CZP 200mg Q2W to placebo as described above for the ASAS40 response, BASDAI, and BASFI at Week 12 and Week 52, for SI joint SPARCC score at Week 12, for ASQoL at Week 52, nocturnal pain score at Week 52, and number of subjects with AU or new AU flares through Week 52 will be part of the fixed sequence testing procedure outlined in Section 14.2.

Additionally, sensitivity analyses will be conducted on these secondary efficacy endpoints. In particular, the assumptions related to missing data will be investigated further. These analyses are described in Section 14.8.

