#### **14.8 Handling of dropouts or missing data**

For analysis purposes, the primary efficacy variable is defined as a composite endpoint in which it is necessary to achieve ASDAS-MI at Week 52 and to remain on randomized double-blind study treatment through Week 52 in order to be considered a responder (see Section 14.3). Because this composite endpoint definition does not allow for a missing response status, no formal method for handling missing data is needed in the primary efficacy analysis. However, in order to assess the impact of various missing data assumptions on the analysis, additional sensitivity analyses of the primary efficacy variable will be performed as follows:

- Including observed data at Week 52: The observed data at Week 52 will be used and analyzed according to randomized treatment, regardless of whether or not the subject is still on his/her randomized double-blind study treatment at that time. Despite efforts to continue to collect data on all subjects (even if they discontinue the double-blind study treatment), there may still be subjects with missing data at Week 52. Such subjects will be considered as non-responders in accordance with the composite endpoint definition outlined above. The same logistic regression model specified for the primary analysis will be used.
- MI: The Markov Chain Monte Carlo (MCMC) method will be used to impute intermittent missing data. The resulting multiply imputed data sets will be monotone missing and will be imputed using monotone regression (assuming a MAR pattern). Note that the MI procedure will be done on the continuous ASDAS variable, which will be dichotomized for the logistic regression analysis. Ankylosing Spondylitis Disease Activity Score data collected following the discontinuation of double-blind study treatment will be treated as missing in the original data set for this sensitivity analysis.
- Tipping point analysis: In this analysis, various assumptions will be made about average outcomes among the subsets of subjects who prematurely discontinued double-blind study

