## 14.10 Determination of sample size

Subjects will be randomized in a 1:1 ratio to the CZP 200mg Q2W and placebo treatment groups. The expected responder rates for ASDAS-MI at Week 52 are 40% and 20% for CZP and placebo, respectively. A total sample size of 300 (150 subjects per treatment group) provides 95% power to detect a statistically significant difference in the ASDAS-MI responder rate at Week 52 between CZP and placebo, using a 2-sided significance level of 0.05.

With Protocol Amendment 4, ASAS40 response at Week 12 was elevated to be the primary efficacy variable for Canada (and any other country where applicable or where requested by Regulatory Authorities); however, the study was fully enrolled at the time of this amendment. The expected responder rates for ASAS40 response at Week 12 are also 40% for CZP and 20% for placebo, which are identical to the assumed response rates cited for ASDAS-MI at Week 52. Therefore, the planned total sample size of 300 would provide 95% power for this variable, as well.

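### Adding baseline ASDAS to the primary logistic model would be a cheap gain in power; the planned test is valid without it

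*Protocol*

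**What the plan says.** Protocol 14.3 estimates and tests the odds ratio for ASDAS-MI response at Week 52 "using a logistic regression model with factors of treatment group, region, and MRI/CRP classification". It leaves the definition of the regions to the IXRS and the SAP, but fixes the covariate list itself. In 14.8, the sensitivity analysis that uses all observed Week 52 data repeats that model: "The same logistic regression model specified for the primary analysis will be used". The observed-case analysis does the same.

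The endpoint is defined in 9.1.1: "ASDAS-Major Improvement (ASDAS-MI): ASDAS reduction (improvement) of" at least 2.0 points from Baseline. Under 14.3 the subject must also remain on double-blind treatment through Week 52. Baseline ASDAS is available: "The ASDAS will be calculated at Screening, Baseline, Weeks 2, 4, 8, 12, 16, 20, 24, 28, 32, 36, 40" and later visits. It is not a stratification factor in 7.10.2 or a listed subgroup in 14.3.

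For continuous endpoints the plan does adjust for the starting value. The ANCOVA in 14.4 reads "The model will include Baseline score, treatment group, region, and MRI/CRP classification", and 14.5 uses the same set of terms.

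**The concern.** ASDAS-MI is a change from baseline cut at 2.0. Every term of the ASDAS is zero or positive, so a subject cannot fall by more than the starting score. Baseline ASDAS therefore bears on the chance of response by construction.

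The entry criteria in 6.1 ("Subjects must have active disease as defined by each of the following at Screening and Baseline") ask for BASDAI of at least 4 and spinal pain of at least 4, but set no ASDAS minimum. CRP at or below the ULN is allowed in MRI-positive subjects. Section 7.10.2 requires at least 20% of randomized subjects in each MRI/CRP class, so at least 0.20 × 300 = 60 are MRI+/CRP-. The MRI/CRP factor splits CRP into two levels and carries nothing about symptom severity. Section 14.3 also lets it be dropped if the model does not converge.

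What is at stake is power in the first test of the fixed sequence in 14.2. If that test fails, none of the ten later tests is performed.

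**Working it through.** **1. The plan's own power.** Inputs from 14.10: 150 per arm, two-sided 0.05, and "The expected responder rates for ASDAS-MI at Week 52 are 40% and 20% for CZP and placebo, respectively".

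- Pooled z: (0.20 − 1.96 × √(2 × 0.30 × 0.70/150)) / √((0.24 + 0.16)/150) = (0.20 − 0.1037)/0.0516 = 1.86, power 96.9%.
- Wald on the log odds ratio: ln(2.667) = 0.981; SE = √(1/36 + 1/24) = 0.2635; 0.981/0.2635 − 1.96 = 1.76, power 96.1%.
- With continuity correction 95.9%; unpooled z 97.2%.

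The stated 95% is met.

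**2. How baseline limits response.** The four symptom weights in 9.1.1 sum to 0.121 + 0.058 + 0.110 + 0.073 = 0.362 per point. The CRP term is "0.579 x (natural logarithm of the (CRP [mg/L] + 1").

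- Lowest baseline ASDAS the entry criteria permit: 0.121 × 4 = 0.484 (spinal pain 4, the other ASDAS items and CRP at 0, BASDAI met through Q1, Q4 and Q5).
- All four items at 4 and CRP 0: 4 × 0.362 = 1.45. Response is impossible.
- All four items at 4 and CRP 2 mg/L: 1.448 + 0.579 × ln 3 = 1.448 + 0.636 = 2.08. Response needs almost no residual activity.
- If CRP does not change, the mean symptom score must fall by 2.0/0.362 = 5.5 points. If CRP falls from 5 to 1 mg/L, that supplies 0.579 × (ln 6 − ln 2) = 0.64, and a mean symptom fall of (2.0 − 0.636)/0.362 = 3.8 is enough.

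Eligible subjects can thus start at or near a score where response is out of reach. The protocol does not let one say how many do.

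**3. Gain from adding baseline ASDAS.** This was simulated with n = 300 and region and MRI/CRP class already in the model. The baseline SD, the slope of the ASDAS fall on baseline, and the discontinuation rates are assumptions.

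*First set:* within-stratum SD 0.7, slopes 0.3 to 0.7, 3,000 trials per scenario, no discontinuation. The squared ratio of mean z, with against without baseline ASDAS, was 1.04, 1.08 and 1.15. Power at 40% versus 20% went from about 97% to 97–98%. At 35% versus 20% it went from 83% to 84–89%. When discontinuation counts as nonresponse (for example 15% on CZP and 50% on placebo), the information gain is about 2% to 10%.

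*Second set:* within-stratum SD 0.8 to 1.0, residual SD of the fall 0.9, 1,500 trials per scenario, 40% versus 20%. Each cell shows power without → with baseline ASDAS.

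| Slope | No discontinuation | 15% CZP / 50% placebo discontinue |
|---|---|---|
| 0 | 97.5% → 97.5% | 97.1% → 97.1% |
| 0.3 | 96.9–97.2% → 97.3–97.6% | 96.1–96.7% → 96.5–96.7% |
| 0.6 | 96.1–97.0% → 97.7–98.6% | 96.1–96.5% → 97.3–97.6% |
| 0.9 | 96.3–96.9% → 99.1–99.5% | 96.5–96.7% → 98.4–98.6% |

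Simulation error is about √(0.97 × 0.03/1500) = 0.4 points on each power.

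**4. Where the gain comes from.** At slope 0.6, SD 0.8 and no discontinuation, the mean log odds ratio goes from 1.013 to 1.178 and its mean SE from 0.273 to 0.299. Mean z rises from 3.694 to 3.917, and (3.917/3.694)² = 1.12. With discontinuation the same scenario gives (3.832/3.702)² = 1.07. The SE goes up, and z improves because the conditional estimate lies further from zero.

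**The case against.** Nothing in 14.3 is wrong or contradictory. The model contains both stratification factors from 7.10.2 and the test is valid under randomization. Chance imbalance in baseline ASDAS is already covered by the type I error rate. Using ANCOVA for continuous change and a stratified model for a responder endpoint is common practice. All of this stands.

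The endpoint also makes everyone who leaves double-blind treatment a nonresponder whatever their ASDAS, which weakens the link to baseline. This stands too, and is why the lower range of 2% to 10% is given.

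Three stronger readings are tempting, and the documents do not support them.

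- A reader might infer that the planned odds ratio is biased or imprecise. The adjusted and unadjusted odds ratios are different quantities, and adjustment raises the SE. The loss is in power.
- A reader might infer that a CRP-negative subject needs a mean symptom score of at least 5.5 to respond. That holds only if CRP does not move. A CRP at or below the ULN can still fall, and the CRP term has the largest coefficient.
- A reader might extend the argument to the ASAS40 models by adding baseline BASDAI. The ASAS40 domains in 9.1.2 are PGADA, total spinal pain, BASFI and the mean of BASDAI questions 5 and 6. Total BASDAI is not one of them and does not cap ASAS40 response, and no calculation supports that change.

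**Conclusion.** This is a cheap improvement to the primary analysis and not an error. The covariate list in 14.3 omits a measured baseline value that limits the outcome by definition. The primary test therefore has somewhat less power than the collected data allow.

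At the planned 40% versus 20% the gain is 0 to about 2 points for slopes up to about 0.7, and about 3 points at a slope of 0.9 without discontinuation. If the true rates were 35% versus 20%, which the protocol does not assume, the gain would be about 1 to 6 points without discontinuation, and less with it. At slope 0 adjustment gains and costs nothing.

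The direction is secure whenever baseline ASDAS predicts response. The size rests on the assumed SD, slope and discontinuation rates, none of which the protocol gives.

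**What to change.** Before the Week 52 unblinding described in 14.9, add continuous baseline ASDAS as a covariate to the primary logistic model in 14.3. Keep the present model as a named sensitivity analysis.

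The FAS in 14.1 does not require a baseline ASDAS, so replace any missing baseline by the overall mean and no FAS subject is dropped. Such a subject has no ASDAS-MI status and is already a nonresponder under 14.3. Since 14.3 has a rule for non-convergence, say in the same place which term is removed first. Leave the ASAS40 models as they are.

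The cost is a line or two of text and no new data. The drawbacks are that the odds ratio becomes conditional on baseline ASDAS, and that the primary model is changed late: 14.10 says enrolment was complete by Amendment 4. The change should be documented as made while still blinded.

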## **4.3 Other immunological variables**

Anti-CZP antibody/anti-drug antibody (anti-CZP Ab/ADAb) concentrations will be assessed at Baseline and Weeks 1, 2, 4, 12, 24, 36, 52/WD, and the FU visit (8 weeks after the Week 52/WD visit). In addition, the anti-CZP Ab concentrations will be assessed in subjects who withdraw from study drug and transition to open-label CZP.

Determination of ADAb will be done using a validated screening, confirmation and titration ADAb bridging assay, with potential further characterization by a neutralizing antibody assay. The immunogenicity data will be processed according to dedicated Bioanalytical Analysis plans.

---

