- Plasma for CZP concentration, anti-CZP antibodies, and for biomarkers at wdt Weeks 0, 4, 12, 24 (and Q12W), 52, and FU

- 
- Gene expression and proteomics at wdt Week 52 only
  - Concomitant medication at wdt Weeks 0, 2, 4, 12, 24 (and Q12W), 52, and FU
  - AEs at wdt Weeks 0, 2, 4, 12, 24 (and Q12W), 52, and FU
  - IXRS (for treatment assignment) at wdt Weeks 0, 2, 4, 12, 24 (and Q12W), 52, and FU
  - CZP administration at wdt Weeks 0, 2, 4, 6, 8, 10, 12, 14, 16, 18, 20, 22, 24, and every 2 weeks thereafter, until Week 52. Loading dose of CZP 400mg at Weeks 0, 2, and 4 must be administered by dedicated site-staff
  - Telephone contact will occur every 4 weeks after the on-site visit at the discretion of the investigator

The following assessments will be applied for subjects who receive an alternative study assessment with other treatment (including biologics) after discontinuation of the double-blind study treatment:

- Blood samples will be collected for hematology and biochemistry analyses, and urine will be collected for urinalysis at wdt Week 0. C-reactive protein analyses will be performed at wdt Weeks 0, 12, 52, and FU

Note: Biochemistry assessment will include the measurement of HbA1c at wdt Week 0

- Physical examination at wdt Week 0 and FU.
- BASDAI, BASFI, total and nocturnal spinal pain, Patient's Global assessment, and Investigator's AS assessment at wdt Weeks 0, 12, and 52
- Swollen and tender joint counts at wdt Week 52 only
- Plasma for CZP concentration, anti-CZP antibodies, and for biomarkers at wdt Weeks 0, 12, and FU
- Concomitant medication at wdt Weeks 0, 12, 24 (and Q12W), 52, and FU
- AEs and IXRS (for the registration of visits) at wdt Week 0, 12, 24 (and Q12W), 52, and FU
- Other treatment administration at wdt Week 0. For Week 12 and 24 (and Q12W) the regimen of the particular medicine should be followed. If the Investigator chooses to withdraw the subject, the local guidelines on initiation and monitoring of the particular treatment should be followed.
- Telephone contact will occur every 4 weeks after the on-site visit at the discretion of the Investigator

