For Canada (and any other country where applicable or where requested by Regulatory Authorities), the primary efficacy variable measurement is the ASAS40 response at Week 12. Analysis of the ASAS40 response at Week 12 will be performed as described above for ASDAS-MI response at Week 52. Similar to the ASDAS-MI efficacy endpoint, the ASAS40 will be treated as a composite endpoint when it is analyzed. Specifically, subjects will need to: 1) achieve the relevant response (ASAS40); and 2) remain in the study and on their randomized double-blind study treatment through Week 12.

Subgroup analyses by age, gender, race, symptom duration, smoking history, HLA-B27 genotype, anti-CZP Ab (ADAb) status, region, prior anti-TNF exposure, Baseline SPARCC score  $\geq 5$ , and MRI/CRP classification (MRI+/CRP+; MRI+/CRP-; MRI-/CRP+) will be performed for the primary efficacy variable. Subgroup analyses will be summarized using descriptive statistics only.

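### Section 14.3 splits the primary variable by anti-CZP antibody status, a post-randomisation result of CZP exposure, so the CZP-placebo contrast by that factor cannot be interpreted for ASDAS-MI at Week 52

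*Protocol*

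**What the plan says.** Section 14.3 names the subgroup factors for the primary efficacy variable: "Subgroup analyses by age, gender, race, symptom duration, smoking history, HLA-B27 genotype, anti-CZP Ab (ADAb) status, region, prior anti-TNF exposure", then Baseline SPARCC score and MRI/CRP class. For ADAb status it gives no time point, no set of samples and no restriction to one arm. It adds: "Subgroup analyses will be summarized using descriptive statistics only".

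Section 4.3 says antibody "concentrations will be assessed at Baseline and Weeks 1, 2, 4, 12, 24, 36, 52/WD, and the FU visit". It also says "the anti-CZP Ab concentrations will be assessed in subjects who withdraw from study drug and transition to open-label CZP", without regard to randomised arm. Section 8.9 gives the open-label sampling times: "Plasma for CZP concentration, anti-CZP antibodies, and for biomarkers at wdt Weeks 0, 4, 12, 24 (and Q12W), 52, and FU".

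The primary endpoint is a composite. Under Section 14.3, "subjects that discontinue the double-blind study treatment prior to Week 52" count as nonresponders, as do those with no ASDAS-MI status at Week 52. Table 7-1 excludes anyone with earlier CZP exposure. Section 7.8.2 requires study treatment to stop before commercial CZP is started.

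For Canada, Section 14.3 makes ASAS40 at Week 12 the primary variable and requires double-blind treatment only through Week 12. Section 14.6.2 separately plans to correlate immunogenicity with PK and efficacy.

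**The concern.** A subgroup comparison between arms is readable when the factor cannot be affected by treatment. Age, HLA-B27, region and Baseline SPARCC score meet that condition. ADAb status does not: one arm receives the drug that induces it, and the other receives that drug only after leaving double-blind treatment. Splitting by ADAb status therefore selects different kinds of subject in the two arms, and the composite rule ties that selection directly to nonresponse.

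At stake is a descriptive table that could show a large CZP-placebo difference in ADAb-positive subjects for reasons unrelated to efficacy. Under some definitions it could also mask a real loss of response in CZP subjects who form antibodies.

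**Working it through.** **Inputs from the protocol (Section 14.10).** 150 subjects per arm, responder rates of 40% (CZP) and 20% (placebo), 2-sided alpha 0.05, stated power 95%. The stated power reproduces: (0.20 − 1.96·√(2·0.30·0.70/150)) / √((0.24+0.16)/150) = (0.20 − 0.1037)/0.0516 = 1.86, which gives 96.9% (95.9% with a continuity correction). Nothing below changes it. The protocol gives no switch, discontinuation or seroconversion rates, so those used below are assumptions.

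**Step 1: who can be placebo and ADAb-positive for ASDAS-MI at Week 52?** Prior CZP is excluded, and a placebo subject can receive CZP before Week 52 only by leaving double-blind treatment. There are two cases.
- *Only double-blind samples count.* The positives are assay false positives or pre-existing reactivity. At an assumed 1%, that is 150 × 0.01 = 1.5 subjects.
- *Open-label samples also count.* The group gains switchers who seroconverted, and each is a nonresponder under the composite.

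In neither case does the group correspond to the CZP ADAb-positive group.

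**Step 2: size in the placebo arm if open-label samples count.** There are 150 × 0.20 = 30 responders, all still on double-blind treatment. Let s be the share who switch and q the share of switchers who seroconvert. Exposure-created positives = 150·s·q, with 0 responders. Rate in negatives = 30/(150 − 150·s·q).

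| s | q | positives created | their rate | rate in negatives |
|---|---|---|---|---|
| 20% | 10% | 3 | 0% | 30/147 = 20.4% |
| 40% | 30% | 18 | 0% | 30/132 = 22.7% |
| 60% | 60% | 54 | 0% | 30/96 = 31.25% |

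The 0% does not depend on s or q. Adding 1% false positives among non-switchers lifts the whole placebo positive group only to between 0.5% and 7.1% over s = 20–60% and q = 10–60%.

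**Step 3: CZP arm, if status means ever positive on drug.** Assume antibodies have no effect on response. Take 40% responders, a share d who stop early (all nonresponders), 30% ADAb-positive among 52-week completers and 10% among early stoppers.
- Rate in positives = 0.40·0.30 / [0.40·0.30 + (0.60−d)·0.30 + d·0.10].
- d = 30%: 0.12/0.24 = 50.0% in positives, 0.28/0.76 = 36.8% in negatives; false gap 13 points.
- d = 20%: 0.12/0.26 = 46.2% against 0.28/0.74 = 37.8%; gap 8 points.
- d = 40%: 0.12/0.22 = 54.5% against 0.28/0.78 = 35.9%; gap 19 points.

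A simulation derived the shortfall in positives from time on drug instead of assuming the 10% and 30%. It used constant seroconversion risk on CZP, 10–60% positive by Week 52 with full exposure, and 10–30% stopping at a uniformly distributed time. Rates were 41.8–46.8% in positives and 33.6–39.7% in negatives, a gap of 2.4 to 12.1 points. When every discontinuer moved to open-label CZP and stayed sampled to Week 52, both rates were about 40% and the gap disappeared.

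**Step 4: the Canadian variable.** A placebo subject on treatment at Week 12 with ASAS40 is a responder. If that subject later switches and turns positive, the placebo ADAb-positive group contains a responder, so the 0% rule does not hold.

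**The case against.** The strongest reply is that Section 14.3 states no definition. It does not say ever positive, does not say open-label samples count and does not say both arms are tabulated. Section 14 leaves detail to the SAP, and Section 4.3 leaves antibody processing to bioanalytical plans. This stands for the CZP-arm bias, which needs a cumulative definition; its size and sign are not fixed by the protocol. It also stands against asserting that the Canadian variable would be classified from samples after Week 12, because no section says so. It does not rescue the between-arm contrast: under either choice of samples in Step 1, the placebo ADAb-positive group has no counterpart role to the CZP one. That follows from the factor chosen, which the protocol does fix.

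The placebo artefact and the CZP-arm bias also coexist only in part. The first needs open-label samples to count. The second shrinks when they do, because CZP subjects who move to open-label CZP remain exposed and sampled. It does not vanish altogether, since discontinuers may go to other treatments instead.

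Finally, the tables are descriptive, and Section 14.6.2 already plans to relate immunogenicity to efficacy. Both points stand. A reader might infer that the primary result is threatened, or that antibody-related loss of response would go unexamined; the documents support neither.

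**Conclusion.** The point holds in a limited form. For ASDAS-MI at Week 52, the CZP-placebo contrast by ADAb status is uninterpretable under either choice of samples, and placebo positives created by CZP exposure have a 0% responder rate whatever the switch and seroconversion rates.

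The CZP-arm distortion is conditional. Under an ever-positive definition and assumed rates it is roughly 2 to 19 points in favour of ADAb-positive subjects, and about nil if all discontinuers continue sampled on open-label CZP. The upper end comes from the assumed 10% and 30% positivity; the simulation reached 12 points.

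One might extend the 0% rule to every version of the primary variable. Step 4 shows that it fails for ASAS40 at Week 12.

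No subgroup analysis enters the fixed testing sequence, so the primary conclusion, type I error and power are unaffected. This is a worthwhile and cheap correction to a descriptive analysis.

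**What to change.** In Section 14.3, delete ADAb status from the list of between-treatment subgroup factors. In Section 14.6.2, describe response by ADAb status as follows:
- within the CZP arm only;
- classified from samples taken on double-blind CZP up to a fixed landmark no later than the endpoint, for example Week 12;
- among subjects still on double-blind CZP at that landmark;
- with samples taken after a switch tabulated separately.

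The cost is protocol and SAP wording and one re-specified descriptive table, with no new samples and no change to sample size. The landmark table leaves out early discontinuers and does not reflect seroconversion after the landmark, and a footnote should say so.
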